5.3. Lifestyle Considerations

No restrictions are required.

5.4. Screen Failures

Screen failures are defined as participants who consent to participate in the clinical study but are not subsequently entered into the study.

Tests with results that fail eligibility requirements may be repeated once during screening if the investigator believes the result to be in error. Additionally, a participant who fails screening may repeat the screening process 1 time if the investigator believes that there has been a change in eligibility status. Participants who rescreen must reconsent and be assigned a new participant number.

5.5. Replacement of Participants

No participants will be replaced at any time during this study.

6. STUDY TREATMENT

6.1. Study Treatment Administered

Information regarding study drug and administration is provided in Table 6. Participants will record study drug administration in a daily diary. Participants will take the study drug once daily, preferably in the morning.

Table 6: Study Treatment Information

Study treatment name:	INCB054707
Dosage formulation:	Tablet
Unit dose strength/dosage level:	INCB054707 15 mg QD
Route of administration:	Oral
Administration instructions:	INCB054707 will be taken orally with water without regard to food.
Packaging and labeling:	INCB054707 will be provided as 15 mg tablets and labeled as required per country requirement.
Storage:	Ambient (15°C-30°C/59°F-86°F)

6.2. Preparation, Handling, and Accountability

The investigator (or designee) is responsible for study treatment accountability, reconciliation, and record maintenance (ie, receipt, reconciliation, and final disposition records). Inventory and accountability records must be maintained and readily available for inspection by the study monitor and are open to inspection at any time by any applicable regulatory authorities. The investigator or designee must maintain records that document:

- Delivery of study drug to the study site.
- Inventory of study drug at the site.
- Participant use of the study drug including tablet counts from each supply dispensed.
- Return of study drug to the investigator or designee by participants.

The investigational product must be used only in accordance with the Protocol. The investigator will also maintain records adequately documenting that participants were provided the specified study drug. These records should include dates, quantities, and any available batch or serial numbers or unique code numbers assigned to the investigational product and participants.

Completed accountability records will be archived by the site. The investigator or designee will be expected to collect and retain all used, unused, and partially used containers of study drug until verified by the study monitor (unless otherwise agreed to by the sponsor). At the conclusion of the study, the investigator or designee will oversee shipment of any remaining study drug back to the sponsor or its designee for destruction according to institutional SOPs. If local procedures mandate on-site destruction of investigational supply, the site should (where local procedures allow) maintain the investigational supply until the study monitor inspects the accountability records in order to evaluate compliance and accuracy of accountability by the investigative site. At sites where the study drug is destroyed before monitor inspection, the monitors rely on documentation of destruction per the site SOP.

Further guidance and information for the final disposition of unused study treatments are provided in the Study Reference Manual.

6.3. Measures to Minimize Bias: Randomization and Blinding

Not applicable. This is an open-label study.

6.4. Study Treatment Compliance

Compliance with all study-related treatments should be emphasized to the participant by the site personnel, and appropriate steps should be taken to optimize compliance during the study. Compliance with INCB054707 will be calculated by the sponsor based on the drug accountability documented by site personnel and monitored by the sponsor/designee using tablet counts. Participants will be instructed to bring all study drug with them to the study visits in order for site personnel to conduct tablet counts to assess study drug accountability. The drug accountability documentation will be used by the sponsor to calculate treatment compliance.

6.5. Dose Modifications

In some circumstances, it may be necessary to temporarily interrupt treatment with INCB054707 as a result of AEs or laboratory abnormalities that have an unclear relationship to the study drug (see Table 7). Except in cases of emergency, it is recommended that any laboratory findings be confirmed and that the investigator consult with the sponsor medical monitor (or other representative of the sponsor) before temporarily interrupting study drug.

Table 7: Guidelines for Interrupting, Restarting, and Discontinuing Study Drug

ADVERSE EVENT	ACTION TAKEN	
Chemistry		
AST and/or ALT > 3.0 × ULN	 Step 1: Interrupt study drug administration up to 2 weeks (14 days) until the toxicity has resolved to ≤ 3.0 × ULN. Step 2: Restart study drug, and monitor as clinically indicated. 	
AST and/or ALT > 5.0 × ULN	Discontinue study drug administration, and monitor as described in Section 9.3.	
Hematology		
Platelet counts 50 to ≤ 100 × 109/L or ≥ 50% decrease from baseline	Step 1: Interrupt study drug administration up to 2 weeks (14 days) until the toxicity has resolved to $> 100 \times 10^9/L$.	
	Step 2: Restart study drug, and monitor as described in Section 9.3.	
$ANC \le 1.0 \times 109/L$	Step 1: Interrupt study drug administration up to 2 weeks (14 days) until the toxicity has resolved to $> 1 \times 10^9/L$ or the baseline value.	
	Step 2: Restart study drug, and monitor as clinically indicated.	
Hemoglobin 8 to ≤ 10 g/dL	Step 1: Interrupt study drug administration up to 2 weeks (14 days) until the toxicity has resolved to > 10 g/dL.	
	Step 2: Restart study drug, and monitor as clinically indicated.	
 Platelet count < 50 × 10⁹/L ANC < 0.5 × 10⁹/L 	Discontinue study drug administration, and monitor as described in Section 9.3.	
• ANC ≤ 1.0 × 10 ⁹ /L with an oral temperature of at least 38.5°C OR with ≥ Grade 3 infection		
• Hemoglobin < 8 g/dL		

Table 7: Guidelines for Interrupting, Restarting, and Discontinuing Study Drug (Continued)

ADVERSE EVENT	ACTION TAKEN	
Other toxicities		
Any Grade 1 or Grade 2 toxicity	Continue study drug and treat the toxicity; monitor as clinically indicated.	
Any Grade 3 toxicity except those that are clearly and incontrovertibly due to underlying disease or extraneous causes	 Step 1: Interrupt study drug up to 2 weeks (14 days), until toxicity resolves to ≤ Grade 1. Step 2: Restart study drug and monitor as clinically indicated. 	
Any other Grade 4 toxicity	Discontinue study drug administration and follow-up as described in Section 8.7.	

Note: The investigator will make an assessment of intensity for each AE and SAE reported during the study and assess severity as described in Section 9.3.

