8.3.5. Laboratory Assessments

8.3.5.1. Safety Assessments

Required laboratory tests are listed in Table 10. Safety laboratory tests include hematology, chemistry, CRP, and lipid panel (see Table 3). Participants may have a light snack before this visit, but should allow for an overnight fast (at least 8 hours) before sample collection for the lipid panel.

If there is any abnormality in hematology assessment (particular for platelet counts) at Week 2, an unscheduled visit at Week 3 (see Section 8.6) to repeat hematology assessments will be required.

Clinical laboratory tests will be performed at a central laboratory (see the Laboratory Manual for sample handling and shipping instructions).

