8.6. Unscheduled Visits

Unscheduled visits may occur at any time at the investigator's discretion, and appropriate clinical and laboratory tests may be performed, as clinically indicated.

If there is any abnormality in hematology assessment (particular for platelet counts) at Week 2, an unscheduled visit at Week 3 to repeat hematology assessments will be required. Refer to Section 6.5 for the instruction of dose interruption and restart. The investigator must inform and consult sponsor with any hematological abnormality.

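### Table 7 stops dosing when platelets halve from baseline but allows restart at any count above 100 × 10⁹/L, so with a baseline above 200 the fall can be unrecovered or worse at restart

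*Protocol*

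**What the plan says.** The platelet row of Table 7 (Protocol Section 6.5) has two interruption triggers joined by 'or': "Platelet counts 50 to ≤ 100 × 109/L or ≥ 50% decrease from baseline". Here 109/L is 10⁹/L.

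- **Step 1** holds drug for up to 14 days and gives a single recovery level, a count above 100 × 10⁹/L. It has no term relative to baseline.
- **Step 2** reads "Restart study drug, and monitor as described in Section 9.3".
- A count below 50 × 10⁹/L leads to permanent discontinuation in a separate row.

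The surrounding text bears on restart as follows:

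- Section 6.5 recommends confirming laboratory findings and consulting the medical monitor "before temporarily interrupting study drug". It does not mention consultation before restarting.
- Section 8.6 is stronger: "The investigator must inform and consult sponsor with any hematological abnormality". For the rule itself it sends the reader back: "Refer to Section 6.5 for the instruction of dose interruption and restart".
- Section 9.3, named in Step 2, covers following an adverse event until it resolves or is judged permanent. It gives no platelet value.
- The ANC row of the same table adds "or the baseline value" to its recovery target.

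**The concern.** A stopping rule and its restart rule should not both be satisfied by the same count. Here the percentage trigger asks for a hold because platelets have halved, yet the only numeric condition for lifting the hold ignores the size of the fall. An investigator who restarts at a count above 100 is following Step 1. One who keeps holding because the count is still at or below half of baseline is following the trigger. Two sites can therefore handle the same count differently, and the less cautious of the two is within the protocol.

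Safety and tolerability is the primary objective, and there is no data safety monitoring board. Platelets are also the one hematology parameter the protocol singles out. Sections 8.3.5.1 and 8.6 both require a repeat at Week 3 "If there is any abnormality in hematology assessment (particular for platelet counts) at Week 2". Adverse events leading to dose interruption are tabulated (SAP Section 8.2.2), so uneven handling would also show in that table.

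**Working it through.** **Inputs**, all counts in 10⁹/L, with baseline *B* and current count *P*:

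- Absolute trigger: 50 ≤ *P* ≤ 100 (Table 7).
- Relative trigger: fall of at least 50%, that is *P* ≤ *B*/2 (Table 7).
- Discontinuation: *P* < 50 (Table 7).
- Restart level: *P* > 100 (Table 7, Step 1).
- Entry: screening counts below 150 are excluded (Section 5.2, criterion 7e), with no upper limit, so baselines above 200 are eligible.

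The baselines below are assumed for illustration, because the documents give no distribution.

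**Step 1: where the relative trigger does any work.** If *B* ≤ 200, then *B*/2 ≤ 100. Every count at or below *B*/2 is then either in 50 to 100, which the absolute trigger covers, or below 50, which means discontinuation. The relative trigger adds nothing. It acts alone only when 100 < *P* ≤ *B*/2, which requires *B* > 200.

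**Step 2: compare with the restart level.** Every count in 100 < *P* ≤ *B*/2 satisfies *P* > 100. So wherever the relative trigger acts alone, the restart level is already met when dosing is interrupted.

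**Step 3: size of the fall at restart.** At *P* = 101 the fall is (*B* − 101)/*B*:

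| Baseline *B* | *B*/2 | Counts that both trigger a hold and meet the restart level | Fall at a count of 101 | Restart level if the fall must also be < 50%: above max(100, *B*/2) |
|---|---|---|---|---|
| 150 | 75 | none | 32.7% | > 100 (unchanged) |
| 200 | 100 | none | 49.5% | > 100 (unchanged) |
| 250 | 125 | 101–125 | 149/250 = 59.6% | > 125 |
| 300 | 150 | 101–150 | 199/300 = 66.3% | > 150 |
| 400 | 200 | 101–200 | 299/400 = 74.8% | > 200 |

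**Step 4: a worked case.** Baseline is 300 and the first low count is 140. The fall is (300 − 140)/300 = 53.3%, so drug is held. Suppose a later sample is needed before restart, which is the kinder reading. The recheck is 105, a fall of (300 − 105)/300 = 65.0%. The count exceeds 100, so Step 1 is met and Step 2 says restart. But 105 ≤ 150, so the interruption trigger is also met. Requiring a recheck delays restart but does not prevent it when the count has worsened.

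**Step 5: look for a rule elsewhere.** Section 8.6 refers restart back to Section 6.5, and Section 9.3 has no platelet value. No other section of either document supplies one.

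**The case against.** The strongest reply is that Step 1 asks for the toxicity to have resolved, and the toxicity in this row includes the halving. A count that moves from 140 to 105 off drug has not resolved on any ordinary reading, so a careful investigator would keep holding. That reading is reasonable, but the text ties resolution to a number that contains no percentage. The reply shows that the cautious reading is available, not that it is the only one.

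A second reply is that the design may be deliberate: pause on a sharp fall, confirm, consult, and resume if the absolute count is safe. With baseline 400, a stable count of 180 is above the entry floor of 150, yet it is a fall of (400 − 180)/400 = 55% and would bar restart under a stricter rule. The clinical point has some force. It does not rescue the row, because a participant restarted at 180 would still meet the trigger for interruption. If that design is intended, the row has to say so.

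Third, there are real safeguards:

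- The table is headed as guidelines.
- Sponsor consultation on hematological abnormalities is mandatory.
- Hematology is drawn at every visit.
- Treatment must stop if continuing would be injurious in the investigator's judgment (Section 7.1.1).
- Counts below 50 end treatment.

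These lower the chance of harm and they stand. None of them states a recovery value for the percentage trigger.

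The ANC row is also a weak comparison. Its baseline value is an alternative route to restart, not an added requirement. It shows only that baseline was considered elsewhere in the table, and the finding does not depend on it.

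**Conclusion.** The point holds. For any baseline above 200 × 10⁹/L, the platelet row's restart level is met by every count at which its percentage trigger acts alone. The row therefore permits restart with the fall unrecovered or deeper: up to 59.6%, 66.3% and 74.8% at a count of 101 for assumed baselines of 250, 300 and 400. At baselines of 200 or below there is no problem.

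The cut-off of 200 follows exactly from the table. How many participants would be affected is unknown, because the documents give neither a baseline platelet distribution nor an expected rate of such falls, and only about 10 participants are planned. No efficacy analysis is affected. What is at stake is participant safety and consistent handling in a study whose primary objective is safety. It should be corrected, with the consultation requirement as a partial safeguard until then. The Investigator's Brochure was not available, so any rationale given there for the level of 100 could not be checked.

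**What to change.** Reword the Step 1 condition in the platelet row to: *until the count is > 100 × 10⁹/L and the decrease from baseline is < 50%*. Restart then needs a count above the larger of 100 and half of baseline, which undoes both triggers. In the worked case (baseline 300) it needs more than 150, so neither 140 nor 105 qualifies. The first whole count that does is 151, a fall of 149/300 = 49.7%.

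The cost is one clause, made by protocol amendment with IRB/IEC approval (Section 11.1). No scheduled visits or samples are added. At baselines of 250, 300 and 400 the restart level rises by 25, 50 and 100, so some participants will stay off drug longer within the existing 14 days, and participants are not replaced (Section 5.5). The row already says nothing about a participant who has not recovered by day 14. The tighter condition does not create that gap, but more participants could reach it, so the amendment is a sensible place to state what happens then.

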5.2. Exclusion Criteria

Participants are excluded from the study if any of the following criteria apply:

- 1. Women who are currently pregnant or lactating.
- 2. Presence of > 20 draining fistulas at screening and baseline.
- 3. Participants with concurrent conditions or history of other diseases, as follows:
 - a. Any clinically significant medical condition other than HS, as determined by the investigator, that is not adequately controlled with appropriate treatment.
 - b. Any other active skin disease or condition (eg, bacterial, fungal, or viral infection) that may interfere with the course, severity, or assessments of HS.
 - c. Active systemic viral infection or any active viral infection that, based on the investigator's clinical assessment, make the participant an unsuitable candidate for the study.
 - d. Current herpes zoster infection, a history of recurrent herpes zoster, a history of disseminated herpes simplex, or a history of herpes zoster.
 - e. History of malignancy, including lymphoma and leukemia within 5 years before baseline, other than a successfully treated nonmetastatic cutaneous squamous cell carcinoma, basal cell carcinoma, or localized carcinoma *in situ* of the cervix.
 - f. Albinism.
- 4. Prolonged QT interval corrected for heart rate using Fridericia's formula (QTcF), defined as ≥ 450 msec.

Note: Prolonged QTcF values of \geq 450 msec at screening are to be confirmed by performing 2 additional ECGs and averaging the results to determine if the averaged value meets the exclusion criterion.

5. Positive test result for TB from the QuantiFERON-TB Gold test, or equivalent, at screening (or, if 2 indeterminate tests or not available, then as evaluated by a purified protein derivative test with a result of < 5 mm of induration within 3 months of screening) or a history of active TB.

Note: If the participant has possible evidence of a latent TB infection, the participant must have documented completion of an adequate course of therapy for latent TB and provide recent (within 3 months) posteroanterior and lateral views chest x-ray without changes suggestive of active or latent TB, prior to baseline.

- 6. Positive serology test results for HIV, HBsAg, HBV core antibody, or HCV (HCV-antibody with positive HCV-RNA) at screening.
- 7. Decreased blood cell counts at screening, defined as follows:
 - a. Leukocytes $< 3.0 \times 10^9/L$ ($< 2.5 \times 10^9/L$ for participants who are African-American).

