 - b. ANC $< 1.5 \times 10^9 / L$.
 - c. Lymphocytes $< 0.8 \times 10^9/L$.
 - d. Hemoglobin < 10 g/dL.
 - e. Platelets $< 150 \times 10^9/L$.

- 8. Severely impaired liver function (Child-Pugh Class C) or ALT or AST levels $\geq 1.5 \times \text{ULN}$.
- 9. Impaired renal function with serum creatinine > 1.5 mg/dL.
- 10. Use of the following medications:
 - a. Previous use of JAK inhibitors, systemic or topical (eg, ruxolitinib, tofacitinib, baricitinib, filgotinib, lestaurtinib, and pacritinib).

Version 1

- b. Previous use of adalimumab or any other TNF-α treatment, investigational, or any experimental treatments within 12 weeks or 5 half-lives (whichever is longer) before baseline.
- c. Systemic immunosuppressive or immunomodulating drugs (eg, oral or injectable corticosteroids, methotrexate, cyclosporine, and azathioprine) within 4 weeks or 5 half-lives (whichever is longer) before baseline.
- d. Other systemic therapies for HS (eg, retinoids and antiandrogens) with potential therapeutic impact for HS within 4 weeks or 5 half-lives (whichever is longer) before baseline.
- e. Surgical, laser, or IPL intervention in area with HS lesion within 4 weeks before baseline.
- f. Systemic anti-infectives (eg, antibiotics, antivirals, antifungals) within 4 weeks or topical anti-infectives on HS lesions (eg, antibiotics, antivirals, antifungals) within 2 weeks before baseline.
- g. Received live vaccine within 6 weeks before baseline or planning to receive live vaccine during the course of the study or within 6 weeks after EOT.
- h. Topical antiseptic washes, creams, soaps, ointments, gels, and liquids containing antibacterial agents to treat HS, except those listed in Sections 6.6.2.3 and 6.6.2.4, within 2 weeks before baseline.
- Potent systemic CYP3A4 inhibitors and inducers (see Appendix B) or fluconazole within 2 weeks or 5 half-lives (whichever is longer) before baseline.
 Note: Topical agents with limited systemic availability are permitted.
- 11. Known or suspected allergy to INCB054707 or any component of the study drug.
- 12. Known history of clinically significant drug or alcohol abuse in the last year prior to baseline.

14. Inability or unlikeliness of the participant to comply with the dose schedule and study evaluations, in the opinion of the investigator.

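### Table 7 tells sites to hold study drug at a hemoglobin of exactly 10.0 g/dL, which the entry criteria accept, and restart needs more than 10

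*Protocol*

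**What the plan says.** Three rules in the protocol bear on the same number.

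- **Entry.** Exclusion criterion 7 (Protocol 5.2) is introduced with "Decreased blood cell counts at screening, defined as follows". Item 7d is "Hemoglobin < 10 g/dL". A screening value of 10.0 g/dL is therefore eligible.
- **Hold.** The hematology part of Table 7 (Protocol 6.5) interrupts study drug, for up to 14 days, at "Hemoglobin 8 to ≤ 10 g/dL".
- **Restart.** The same row keeps the drug on hold "until the toxicity has resolved to > 10 g/dL". It offers no other route back. The ANC row of the same table does, because it also accepts "or the baseline value" as resolution.

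Below 8 g/dL the drug is discontinued.

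The surrounding text is softer than the row. Table 7 is titled "Guidelines for Interrupting, Restarting, and Discontinuing Study Drug". Section 6.5 is framed around events and laboratory abnormalities whose link to study drug is uncertain. It adds that, emergencies aside, "it is recommended that any laboratory findings be confirmed" and the medical monitor contacted before a hold. Section 8.6 goes further: "The investigator must inform and consult sponsor with any hematological abnormality".

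**The concern.** A hold rule is meant to react to a change after dosing. Here the upper end of the hold range is a value that the protocol accepts before dosing. Read literally, a participant enrolled at 10.0 g/dL meets the hold at the first on-treatment blood count that shows no change. Going back to the entry value does not release the hold.

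At stake is a treatment decision for someone with no toxicity. Either the site follows the row and stops the drug, or the site and sponsor set the row aside case by case. In a study whose primary objective is safety and tolerability, the written rule should give the right answer without improvisation.

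**Working it through.** No figure in the plan needs reproducing. The check sets the rules side by side.

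**Step 1: the hemoglobin rules on one scale.** Inputs are exclusion 7d and the Table 7 hemoglobin row.

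- Eligible at screening: Hb ≥ 10
- Hold: 8 ≤ Hb ≤ 10
- Restart: Hb > 10

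The documents do not state the reporting precision, so I assume one decimal place.

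| Hb (g/dL) | Eligible at screening | Hold met | Restart met |
|---|---|---|---|
| 9.8 | no | yes | no |
| 9.9 | no | yes | no |
| **10.0** | **yes** | **yes** | **no** |
| 10.1 | yes | no | yes |
| 10.2 | yes | no | yes |

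Only 10.0 is eligible, held and barred from restart. The hold and restart rules agree with each other, since one ends where the other begins. The mismatch is between that shared boundary and the entry limit.

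**Step 2: the other laboratory rows.** Inputs are exclusions 7b, 7e and 8, and the matching rows of Table 7.

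| Test | Eligible | Hold (absolute limit) | Gap between limits |
|---|---|---|---|
| Platelets (10⁹/L) | ≥ 150 | ≤ 100 | 150 − 100 = 50 |
| ANC (10⁹/L) | ≥ 1.5 | ≤ 1.0 | 1.5 − 1.0 = 0.5 |
| ALT/AST (× ULN) | < 1.5 | > 3.0 | 3.0 − 1.5 = 1.5 |
| Hemoglobin (g/dL) | ≥ 10 | ≤ 10 | 10 − 10 = 0, both limits include 10 |

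The platelet row also has a relative trigger, a fall of at least 50% from baseline. An unchanged participant shows a fall of 0% and does not meet it. In every row except hemoglobin, a participant unchanged from an eligible screening value cannot meet the hold.

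**Step 3: the rules after the proposed edit.** With hold at 8 ≤ Hb < 10 and restart at Hb ≥ 10, the value 10.0 is eligible, is not held and satisfies restart. At 9.9 and below the hold still applies, and at 10.1 and above nothing changes. No value meets hold and restart together, and none from 8 upward meets neither.

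**The case against.** The best defense is that the protocol does not intend such a hold and gives sites means to avoid it. Section 6.5 speaks of abnormalities with an uncertain link to study drug, and a value already present before the first dose fits that description poorly. The table's first column is headed as adverse events, its restart wording refers to a toxicity, and conditions present at consent belong in medical history (Protocol 8.3.1 and 9.3). Confirmation is recommended and sponsor consultation on hematology is mandatory.

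This stands as mitigation: a sensible site and monitor would probably not hold the drug. It does not resolve the wording. The row sets an absolute limit without reference to baseline, confirming a true 10.0 returns 10.0 again, and consultation is a procedure with no stated outcome.

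A reader might infer more than the documents support in three ways.

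- **Distorted safety results.** With about 10 participants, one hold counted as an interruption because of a TEAE (SAP 8.2.2) would move that line by 1/10, or 10 percentage points. That is true of any single event at this sample size. It also needs a boundary value, a hold despite consultation, and recording as an adverse event although Protocol 9.1 leaves out expected fluctuations that do not worsen. The chain is remote.
- **Frequent holds from ordinary variation near 10.** The documents give neither a hemoglobin distribution nor a within-person SD. Variation around a cut-off would cause holds wherever the cut-off sits, so it does not measure this error.
- **A known loss of treatment time.** Table 7 limits the hold to 14 days but does not say what follows if a laboratory value has not resolved by then. Neither a 14-day cap on lost treatment nor a permanent stop can be read from it.

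**Conclusion.** Wrong as written, minor. The entry rule and the hold rule both claim the value 10.0 g/dL, and the restart rule shuts it out. That follows from the inequality signs alone and needs no assumption about the data. Its reach is one reported value, assuming one-decimal reporting, and it may affect no participant. The scope wording, confirmation and consultation may prevent the hold in practice, but no rule states this. The point does not call the safety analysis into question.

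**What to change.** In the hemoglobin row of Table 7:

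- change the interruption trigger to *8 to < 10 g/dL*;
- change the restart condition to *≥ 10 g/dL*;
- keep discontinuation at < 8 g/dL.

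Borrowing the ANC row's baseline alternative may look attractive but is not advised. Exclusion 7 is tested at screening, hematology is repeated on Day 1 (Protocol Table 3), and SAP 4.1.3 takes the last value before the first dose as baseline. A participant at 9.8 on Day 1 who stays at 9.8 would then meet hold and restart at once.

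The cost is two wording edits in one row. Protocol 11.1 requires IRB/IEC approval of amendments, so they are best bundled with the next one. The SAP does not change. The only clinical downside is that there is no hold at exactly 10.0 g/dL, a value already accepted at entry. The edit does not create a gap between the entry and hold limits like those in the other rows, and holds caused by small falls below 10 would continue.
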